**Inclusion/Exclusion:** All adult ( $\geq 19$  years) patients who sought primary care for their hip or knee pain of any duration at participating sites were invited to meet with the RA to discuss participating in the study. Potential participants were excluded if: they reported not being able to understand, read, and write English; they had known cancer causing their hip or knee pain; or they reported being unable to complete the scheduled follow-up surveys over the one-year study period. The inclusion criteria for primary care sites were to have at least 1,500 rostered patients and two or more family physicians. Those sites that already had physiotherapy services or not enough space to include the physiotherapist were excluded.

**Study Power:** Participants were recruited over a 13-month period at all 14 primary care sites (7 PT-led arm, 7 usual care arm). Our power calculation is based on methods described by Hemming et al. Our sample size calculation is targeted to detect a clinically meaningful mean difference of 9 points on the Lower Extremity Functional Scale (LEFS) using a two-sided alpha of 0.05, assuming a conservative standard deviation of 16, a conservative intracluster correlation coefficient of 0.1, a cluster autocorrelation coefficient of 0.5, an individual autocorrelation coefficient of 0.6, and a coefficient of variation of 0.7. Allowing for an attrition of 20% of patient participants at the 12-month follow-up, we require a sample size of 560 participants to achieve  $>80\%$  power. Pilot work for this study suggested we would recruit 1 patient per week per site; as such, we planned and prepared resources to recruit approximately 728 participants.

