**Data Analysis Plan**

All analyses will be by intention to treat principle. Descriptive statistics will be provided for baseline characteristics and outcomes using means (standard deviation) or medians (interquartile range) for continuous variables and frequencies (percent) for categorical variables. We will compare arms using linear mixed models and generalized estimating equations (GEE) to account for clustering and present the corresponding p-values. Analyses will be performed using SAS, version 9.4 (SAS Institute Inc; Cary, NC).

The estimand for patient health outcomes will be the time-specific patient participant treatment effect, adjusting for clustering by primary care site. The primary outcome (LEFS) will be analyzed using linear mixed regression with restricted maximum likelihood (REML) estimates under the assumption of Missing at Random (MAR), which will allow the use of all available data without the need for multiple imputation. The Kenward-Rogers degrees of freedom correction will be used to account for a small number of clusters. The 12-month timepoint will provide the intervention effect as the adjusted least square mean difference between arms with 95% confidence intervals. Secondary comparisons will be made using adjusted least square mean differences between arms at all intermediate time-points. Fixed effects in the mixed model will include time, intervention group by time interaction (omitting the group main effect), pre-specified covariates associated with hip and knee function (patient participant age, sex, duration of current episode of hip or knee pain, income, highest level of education, and comorbidity score), and primary care site rurality and number of active patients (the covariates from the covariate-constrained allocation procedure). Repeated measures will be modeled using a covariance structure determined by information criteria (AIC/BIC). Clinic site will be included as a random effect to account for site clustering. We will assess for potential risk of bias associated with missing data by comparing the characteristics of those who participated. We plan to carry out a sensitivity analysis for a potential departure of our MAR assumption using a delta-adjusted imputation pattern mixture model approach. This approach will allow us to investigate the robustness of our trial outcomes with regard to the missing values of the LEFS.

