We plan a secondary analysis using our primary outcome (LEFS) to compare the proportion of participants who experience a meaningful improvement in each arm (responder analysis). We will define a meaningful change as an improvement of greater than or equal to 9 points on the LEFS (the minimally important change). We will present the proportion of participants who experience a meaningful improvement in each arm and compare, using relative risk, between groups using robust Poisson regression, accounting for clustering. We will use empirical covariance (“sandwich”) bias-adjusted (residual-based) estimators, and apply the Fay and Graubard correction for the small number of clusters.

Pain intensity (NPRS), quality of life (EQ-5D-5L), self-efficacy (PSEQ), catastrophic thinking (PCS), pain-related fear (TSK)-11, and depressive symptoms (PHQ-2) will be analyzed using the same analytic approach as described for our primary LEFS analysis, adjusted for the same covariates. We will use simple mean imputation to fill in missing individual items on surveys as described by Chavance. Patient satisfaction and global rating of change do not include a baseline measure and will be assessed using ordinal logistic regression with random effects and adjusting for the same covariates as above.

Incidence rates for minor adverse events (yes or no) will be calculated using robust Poisson regression and compared by calculating relative risks with confidence intervals using GEE-type robust covariance estimators (PROC GLIMMIX, EMPIRICAL option in SAS) to account for clustering. In our models comparing incidence rates, we will use an exchangeable working correlation matrix, empirical covariance (“sandwich”) bias-adjusted (residual-based) estimators, and the Fay and Graubard correction

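### The LEFS responder analysis names no visit and no rule for missing LEFS, so by default it is a complete-case analysis that ignores earlier scores the primary model uses

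*Combined protocol and SAP*

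**What the plan says.** All references are to the Data Analysis Plan of the combined protocol and SAP unless stated otherwise.

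- General principle: "All analyses will be by intention to treat principle".
- Primary LEFS analysis: a linear mixed model fitted by REML under MAR, "which will allow the use of all available data without the need for multiple imputation". The 12-month contrast gives the intervention effect.
- Missing-data sensitivity: a "sensitivity analysis for a potential departure of our MAR assumption using a delta-adjusted imputation pattern mixture model approach", described in the paragraph on the primary LEFS model and aimed at missing LEFS values.
- Responder analysis, called secondary: "We will define a meaningful change as an improvement of greater than or equal to 9 points on the LEFS". The proportions are presented by arm "and compare, using relative risk, between groups using robust Poisson regression, accounting for clustering", with bias-adjusted sandwich estimators and the Fay and Graubard correction.
- The only imputation described alongside the responder and other secondary outcomes is mean imputation of single missing questionnaire items.
- Study Power: "Allowing for an attrition of 20% of patient participants at the 12-month follow-up", 560 participants are required; resources were prepared for about 728.

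The responder paragraph does not give the visit at which improvement is scored, the classification of a participant with no LEFS at that visit, or the covariates. It also does not say whether the delta-adjusted analysis extends to the relative risk.

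**The concern.** The mixed model and the Poisson model use incomplete participants differently. In the mixed model, someone who answers at 3, 6 and 9 months but not at 12 still informs the 12-month estimate through the within-person correlation. A Poisson regression on one yes/no value per person has no such route: with no LEFS at the scored visit there is no outcome, and standard software leaves the row out. The MAR statement therefore does not carry over, and the intention-to-treat sentence does not say how a missing status is classified.

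Participants are not blinded (Strategies to Mitigate Bias), so reasons for not answering could plausibly differ between the models of care. The responder result and the mean difference come from the same LEFS scores. They could disagree merely because they treat withdrawals differently, and the rule would be chosen after the data are seen.

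**Working it through.** **The plan's own figure.** The documents give no number for the responder analysis, so the check starts from the sample size. Inputs from Study Power: difference 9, SD 16, ICC 0.1, cluster autocorrelation 0.5, individual autocorrelation 0.6, CV 0.7, 14 sites, attrition 20%.
- Completers: 560 × 0.8 = 448, so 32 per site and 224 per arm.
- Design effect: 1 + ((1 + 0.7²) × 32 − 1) × 0.1 = 5.668.
- Baseline correlation of site means: r = (32 × 0.1 × 0.5 + 0.9 × 0.6) / (1 + 31 × 0.1) = 0.522.
- SE = √(2 × 16² × 5.668 × (1 − 0.522²) / 224) = 3.07.
- Power = Φ(9/3.07 − 1.96) = 83% by normal approximation. The stated 560 for more than 80% power is reproduced.

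**Participants affected.** 0.20 × 560 = 112; at the recruitment target, 0.20 × 728 ≈ 146. This is anyone without LEFS at the scored visit, including people with earlier follow-up scores.

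**Simulation A.** SD 16 and within-person correlation 0.6, reading the individual autocorrelation as the within-person correlation. Assumed: usual-care gain of 6 points, 12-month responder visit, and 20% missing at 12 months depending on the observed 9-month change (log-odds 0.03 to 0.06 per LEFS point). There were 400,000 participants per arm. Site clustering was left out because the target is bias, not precision.
- SD of change: 16 × √(2 × (1 − 0.6)) = 14.3.
- Usual-care responders: Φ((6 − 9)/14.3) = 0.417. With a 4-point benefit: Φ((10 − 9)/14.3) = 0.528. True RR = 0.528/0.417 = 1.27.

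| Dropout pattern | Complete-case RR, true RR 1.00 |
|---|---|
| Follows poor change in the PT arm only | 1.04 to 1.07 |
| Follows poor change in usual care only | 0.94 to 0.97 (rerun at the steepest slope: 0.93) |
| Poor responders leave the PT arm, good responders leave usual care | 1.08 to 1.16 |
| Same relation in both arms | about 1.00; each proportion 1.6 to 3 points too high |

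With the 4-point benefit, the one-arm patterns and the opposite pattern in the table give 1.18 to 1.44 against 1.27. The same relation in both arms gives 1.25 to 1.26. Imputation from all waves is within 0.01 of the truth throughout.

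**Simulation B.** Different assumptions: correlation 0.1 × 0.5 + 0.9 × 0.6 = 0.59, SD of change 14.5, mean gains 5 and 14. Responders are 39.1% and 63.5%, true RR 1.62.

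| Dropout (usual care / PT) | Complete case | Dropouts counted as non-responders | MAR imputation |
|---|---|---|---|
| 25% / 15%, unrelated to LEFS | 1.62 | 1.84 | 1.62 |
| 15% / 25%, unrelated to LEFS (closed form) | 1.62 | 1.43 | not run |
| 20% / 20%, poor change, same slope | 1.58 | 1.58 | 1.62 |
| 25% / 15%, poor change, same slope | 1.55 | 1.76 | 1.62 |
| 20% / 20%, poor change in usual care, good change in PT | 1.47 | 1.46 | 1.61 |

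With no true effect (gain 5 in both arms), the last pattern gives a complete-case RR of 0.87 and 0.99 by imputation. The MAR mean difference stayed within 0.1 point of the simulated truth in all of these runs.

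**Size against precision.** Var(log RR) ≈ 2 × (1 − p)/(p × 224) × design effect, with p = 0.417. For an assumed responder ICC of 0.02 the design effect is 1 + 46.68 × 0.02 = 1.93 and the SE 0.16; for 0.10 they are 5.668 and 0.27. The 95% interval around RR 1.00 is then 0.74 to 1.36, or 0.59 to 1.68. A shift to 1.07 is 0.25 to 0.44 SE; a shift to 1.16 is 0.56 to 0.96 SE.

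**The case against.** The plan never says that these participants are dropped. It is silent, and counting them as non-responders or imputing them would also fit the text. That stands: exclusion is the default consequence of the model, not a stated rule. The silence still matters, because Simulation B shows that the three readings can give different relative risks.

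A reader might also infer that unequal dropout between arms is enough to bias the relative risk. It is not. Dropout at 25% and 15% unrelated to LEFS leaves the complete-case value at 1.62. The shift needs dropout related to LEFS response, and is material mainly when that relation differs between arms.

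The delta-adjusted analysis is meant to test robustness to missing LEFS values, and responder status comes from LEFS. It could be read as covering the relative risk, but the text neither says so nor excludes it. The plan also compares participant characteristics to assess missing-data bias. That may reveal a problem but does not correct the estimate.

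The dropout slopes, gains and opposite-direction pattern have no source in the documents. The 20% is a planning allowance, and Data Collection and Management describes frequent reminders and phone or in-person completion. The simulated biases at a true RR of 1.00 are below one standard error. All of this stands, and it limits the weight of the point.

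**Conclusion.** The point holds in a limited form. The responder analysis lacks a visit and a rule for missing LEFS. Run as written, it would omit about one participant in five at the planned attrition and rest on a stronger missing-data assumption than the primary model. Responder proportions would be overstated by about 1.6 to 3 points if poor responders leave both arms alike. The relative risk, at a true value of 1.00, would move to about 0.94 to 1.07 if the relation acts in one arm, and to 1.16 or 0.87 in the extreme opposite-direction case. These sizes depend on assumed slopes and gains, 20% missing and a 12-month responder visit, which the plan does not state.

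A reader might take this as a threat to the trial's main result. The documents do not support that: the analysis is labelled secondary, and the 12-month mean difference comes from the mixed model, which is unaffected. The change is still worth making before analysis, because a better method is available and the plan already foresees imputing LEFS.

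**What to change.** In the responder paragraph of the Data Analysis Plan:

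1. Name 12 months as the responder visit, to match the primary time point.
2. Derive responder status from LEFS multiply imputed under MAR. Use the imputation model behind the "delta-adjusted imputation pattern mixture model approach" with delta set to 0, including arm, all LEFS waves, the covariates of the primary model and site.
3. Fit the robust Poisson model with the small-sample correction in each completed dataset and pool. State which covariates it contains.
4. Keep the complete-case relative risk as a sensitivity analysis.
5. State that the delta-adjusted analysis also covers the relative risk.

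The cost is SAP wording and some programming; no new data are needed. At the version date data collection was still under way and analysis was to start only after it ended, so the change could be pre-specified then. The downside is that the responder result then rests on an imputation model, which the plan does not yet specify and which must represent site with only 14 sites, seven per arm.

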to account for small number of clusters. Given that we have only included 14 clusters and adverse events are expected to be rare, we anticipate there may be issues of non-convergence or instability in our models. Should the model for adverse events not converge or demonstrate instability, we would attempt to fit the model using an independent working correlation matrix. If there are still issues of non-convergence or instability, we will reduce the model by removing covariates, beginning with duration of pain and income. Severity and duration of minor adverse events will be presented descriptively. We do not anticipate many, if any, serious adverse events; as such, we plan to present these data descriptively.

Visits with primary care physicians or nurse practitioners, time (days) lost from occupational activities, and assistance required (hours) will be presented as rates and compared by calculating rate ratios using GEE-type covariance estimators with an adjusted Poisson or negative binomial model, accounting for clustering, and assuming an exchangeable working correlation matrix. Incidence rates will be used to present visits to other health professionals within the primary care team, participation in group programs offered by the primary care team, and health care services received outside of the primary care team (medications, diagnostic imaging, walk-in clinic visits, ED visits, specialist physician visits, , hospital admissions, interventional procedures, surgeries, other health provider visits). Comparisons between groups for each of these variables will be made by calculating relative risk using robust Poisson regression. These models will incorporate empirical covariance (“sandwich”) bias-adjusted (residual-based) estimators, and the Fay and Graubard correction due to the small number of clusters. These models will use time as an offset to account for variable follow-up times. All of the healthcare utilization and lost time from occupational activity models will control for the same covariates as the patient health outcomes analyses. Similar to our analyses for adverse events, in the case of model non-convergence or instability, we will attempt to fit the model using an independent working correlation matrix and if the model still does not converge and demonstrate stability, we will reduce the model by removing covariates.

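### The secondary LEFS responder model has no baseline LEFS term. At the plan's own correlations, adding one improves precision, but the gain depends on the ICC and the cluster autocorrelation

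*Combined protocol and SAP*

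**What the plan says.** The responder paragraph of the Data Analysis Plan calls a change meaningful if it is "an improvement of greater than or equal to 9 points on the LEFS". It promises the proportion in each arm and will "compare, using relative risk, between groups using robust Poisson regression, accounting for clustering", with bias-adjusted sandwich estimators and the Fay and Graubard correction. It names no covariate, working correlation or time point.

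The primary LEFS model is more fully specified. It is a repeated-measures mixed model with time and "intervention group by time interaction (omitting the group main effect"). Its individual covariates are "patient participant age, sex, duration of current episode of hip or knee pain, income, highest level of education, and comorbidity score", and it adds site rurality and number of active patients. Baseline LEFS is not on that list.

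For the incidence-rate models the plan says "we will use an exchangeable working correlation matrix". Its fallbacks for non-convergence ("we would attempt to fit the model using an independent working correlation matrix", then "we will reduce the model by removing covariates, beginning with duration of pain and income") are written for adverse events and extended to the utilization models. None is stated for the responder model.

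Study Power assumes "a conservative intracluster correlation coefficient of 0.1, a cluster autocorrelation coefficient of 0.5, an individual autocorrelation coefficient of 0.6". It powers the mean difference and sets no target for the responder comparison.

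**The concern.** Response is a dichotomised change from baseline. If one arm starts higher by chance, regression to the mean lowers its chance of improving by 9 points, and the RR moves against it. The primary model has a device for baseline, since leaving out the group main effect gives the arms a common baseline mean. A single binary outcome per participant has no baseline record in the model, so that device cannot be used. Reading the primary covariate list into the responder model would not help either, because baseline LEFS is not on it.

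The stake is the precision of a secondary result that clinicians are likely to read beside the primary one. With seven sites per arm, chance differences in baseline are not negligible, and the allocation constrained rurality and number of active patients, not LEFS. If an imbalance appears and adjustment is added only then, it will look post hoc.

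**Working it through.** **Inputs from Study Power.** SD 16; ICC 0.1; cluster autocorrelation (CAC) 0.5; individual autocorrelation (IAC) 0.6; coefficient of variation 0.7, taken as that of cluster size; 7 sites per arm; 560 participants (40 per site); 20% attrition (448 completers, 32 per site); effect 9 points; two-sided alpha 0.05.

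**Assumptions not in the documents.** Responder status at 12 months; mean usual-care gains of 5, 9 or 12 points (response 39%, 50% or 58%); normal, unbounded LEFS; allocation treated as unconstrained in the simulations.

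**1. The plan's own figure.** Design effect = 1 + (1.49 × 32 − 1) × 0.1 = 5.668. Correlation of site means over time = (32 × 0.1 × 0.5 + 0.9 × 0.6)/(1 + 31 × 0.1) = 0.522, so the variance factor is 1 − 0.522² = 0.728. SE = √(2 × 256/224 × 5.668 × 0.728) = 3.07. Power by normal approximation = Φ(9/3.07 − 1.96) = 83.4%. The stated power above 80% reproduces.

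**2. Chance baseline difference between arms.**
- 40 per site, equal sites: 16 × √((2/7)(0.1 + 0.9/40)) = 2.99 points.
- 40 per site, CV 0.7: 16 × √((2/280)(1 + (1.49 × 40 − 1) × 0.1)) = 3.54.
- The same formulas at 32 per site: 3.06 and 3.60.

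**3. RR without a baseline term (no true effect, PT arm 1 SD higher).** Correlation of site means at 40 per site = (0.1 × 0.5 + 0.9 × 0.6/40)/(0.1 + 0.9/40) = 0.518, so change falls by 0.48 points per point of imbalance. Correlation within a participant = 0.05 + 0.54 = 0.59, so the SD of change = 16 × √(2 × 0.41) = 14.5. The shift is 0.48 × 2.99 = 1.44 points. At 50% response, RR = Φ(−1.44/14.5)/0.5 = 0.92. At 39% and 58% it is 0.90 and 0.93. With CV 0.7 the three values are 0.89, 0.91 and 0.92. The opposite imbalance gives 1.10, 1.08 and 1.07 with equal sites.

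**4. RR with the term.** Poisson GEE was simulated with the Fay and Graubard correction and a t reference on 12 df. With continuous baseline LEFS added, the RR at +1 SD is 0.98 to 1.00.

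**5. Power at a 9-point effect, without → with the term** (3,000 datasets per scenario, 20% missing at random):

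| Sites | Working correlation | 39% | 50% | 58% |
|---|---|---|---|---|
| Equal | Exchangeable | 68.9 → 78.1 | 67.7 → 77.9 | 65.9 → 75.6 |
| Equal | Independence | 68.8 → 79.2 | 67.7 → 79.0 | 65.6 → 76.4 |
| CV 0.7 | Exchangeable | 62.4 → 70.0 | 64.1 → 71.5 | 63.3 → 70.3 |
| CV 0.7 | Independence | 55.8 → 67.1 | 57.5 → 67.4 | 57.4 → 66.2 |

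A separate simulation at 32 completers per site gave gains of 5.2 to 10.4 points.

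The RR shift and the lost power are one variance seen twice. At 50% response with equal sites, removing the shift from the SD of log RR gives √(0.181² − ln(0.919)²) = 0.160, against a simulated 0.161 with the term.

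**6. Type I error.** It was 3.4% to 6.3% without the term and 4.0% to 7.3% with it. The highest values came at CV 0.7 and 39% response: 5.9% to 6.3% without, 6.7% to 7.3% with.

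**7. Dependence on ICC (CAC 0.5).**
- ICC 0.05: baseline SD 2.3 and RR 0.93 to 0.95 without the term (equal sites, 40 per site). Power gain about 4 to 8 points.
- ICC 0.02: baseline SD 1.8 and RR 0.95 to 0.96 (same basis). Power gain about 2 to 4 points.

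**8. Dependence on CAC (ICC 0.1).** At CAC 0.5, change regresses on baseline with a slope of about −(1 − 0.5) = −0.5 between sites and −(1 − 0.6) = −0.4 within sites, so one individual-level term removes most of both. At higher CAC the between-site slope is flatter and the same term over-adjusts.
- CAC 0.8: RR at +1 SD is 0.95 to 0.96 without and about 1.02 to 1.03 with. The power change ranged from −1.7 points (89.0% → 87.3%) to +3.2 (82.8% → 86.0%) across runs.
- CAC 0.95: RR about 0.98 without and 1.05 to 1.06 with. Power 0 to 4 points lower.

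**The case against.** The strongest reply is that this is an efficiency choice and not an error. An unadjusted RR is a legitimate marginal summary beside the per-arm proportions, its type I error is acceptable, and the analysis is secondary with no power target. All of that stands, and it limits the point to a precision improvement.

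The second reply is that the benefit rests on CAC 0.5. Study Power calls the SD and ICC conservative but does not say so of CAC. This also stands: step 8 shows the gain disappearing, then reversing slightly, as site means become more stable over time. A reader might infer that a baseline term always holds the RR near 1 or always buys power. The calculations do not support that.

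Two smaller replies also stand. The power gains at CV 0.7 are not corrected for the slightly higher type I error at 39% response. And the constrained allocation could reduce the imbalance: if its two covariates explained an assumed 25% to 50% of between-site baseline variance, 2.99 points would become 2.67 to 2.30.

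A reader might also infer that the primary model fully absorbs the imbalance that this one does not. That has not been shown. The primary model has a random site effect but no stated site-by-time term, and how completely it removes site-level baseline differences at CAC 0.5 was not computed.

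**Conclusion.** The point holds as a conditional precision improvement to a secondary analysis. The responder model has no baseline LEFS term and nothing in the plan takes its place. At the plan's ICC and CAC, a one-SD chance imbalance moves the RR by roughly 7% to 11%, and the term removes nearly all of that and adds about 5 to 11 points of power. These sizes rest on the planning correlations and on an assumed usual-care response of 39% to 58%.

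Three stronger readings are not supported. The omission is not a bias averaged over randomizations, since imbalance in either direction is equally likely by chance. It does not touch the primary LEFS result. And one SD here means the between-arm difference of about 3 to 3.6 points, not the participant-level SD of 16.

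The change is worth making because baseline LEFS is already collected and the plan's own values favour it. Confidence is medium because the true CAC is unknown.

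**What to change.** Before outcomes are analysed by arm:
- Pre-specify continuous baseline LEFS as a covariate in the responder Poisson model.
- State the working correlation. Exchangeable would match the plan's other Poisson comparisons.
- Keep the Fay and Graubard correction.
- Still present the unadjusted responder proportions by arm.
- Record the change in the registry and the final publication, as Protocol Amendments requires.

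State too whether the primary covariate list applies. In simulations that assumed six individual covariates explaining 30% of stable individual variance plus two site covariates, type I error was above nominal either way: 6.4% to 8.2% with the list and 6.9% to 9.0% with the list plus baseline LEFS.

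Costs:
- It is a late, documented change to a secondary analysis. The plan is dated November 20, 2025, and analysis starts after data collection ends.
- The term adds one parameter. At least 99.9% of simulated fits converged with it as the only addition.
- With an exchangeable correlation, the adjusted RR for a true effect is slightly closer to 1 (1.43 against 1.47 at 50% response; 1.57 against 1.64 at 39%).
- Type I error may reach about 7% with very unequal sites and 39% response, against about 6% without the term.
- There is little or no gain if site means are much more stable over time than CAC 0.5 implies.
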